**Table 14.3.2.14.1.1**  
**Adverse Events of Special Interest (AESI) Ongoing On Day 1 of Dosing (Pre-existing Adverse Events) by System Organ Class and Preferred Term Safety Population**

System Organ Class / Preferred Term	AD (N= )		bvFTD (N= )		All Subjects (N= )	
	Subjects 	Events	Subjects 	Events	Subjects 	Events
Subjects Reporting at Least One AESI	n (%)	n	n (%)	n	n (%)	n
System Organ Class 1	n (%)	n	n (%)	n	n (%)	n
Preferred Term 1	n (%)	n	n (%)	n	n (%)	n
Preferred Term 2	n (%)	n	n (%)	n	n (%)	n
.						
System Organ Class 2	n (%)	n	n (%)	n	n (%)	n
Preferred Term 1	n (%)	n	n (%)	n	n (%)	n
Preferred Term 2	n (%)	n	n (%)	n	n (%)	n
.						

 At each level of summation (any AESI, system organ class, preferred term), subjects reporting more than one adverse event are counted only once.

path\t\_program.sas date time

*Programming Note: Repeat table for the tables listed below*

*Table 14.3.2.14.1.2 Adverse Events of Special Interest (AESI) Ongoing On Day 1 of Dosing (Pre-existing Adverse Events) by System Organ Class and Preferred Term – Non-AChEI/Memantine Users (Safety Population)*

*Table 14.3.2.14.2.1 Adverse Events of Special Interest (AESI) that Started On or After Day 1 of Dosing (Study-emergent Adverse Events) by System Organ Class and Preferred Term (Safety Population)*

*Table 14.3.2.14.2.2 Adverse Events of Special Interest (AESI) that Started On or After Day 1 of Dosing (Study-emergent Adverse Events) by System Organ Class and Preferred Term – Non-AChEI/Memantine Users (Safety Population)*

*Table 14.3.2.14.3.1 Adverse Events of Special Interest (AESI) (Pre-existing Adverse Events and Study-emergent Adverse Events) by System Organ Class and Preferred Term (Safety Population)*

*Table 14.3.2.14.3.2 Adverse Events of Special Interest (AESI) (Pre-existing Adverse Events and Study-emergent Adverse Events) by System Organ Class and Preferred Term – Non-AChEI/Memantine Users (Safety Population)*

**Table 14.3.2.15.1**  
**Post-Treatment Adverse Events by System Organ Class and Preferred Term**  
**Safety Population**

System Organ Class / Preferred Term	AD (N= )		bvFTD (N= )		All Subjects (N= )	
	Subjects 	Events	Subjects 	Events	Subjects 	Events
Subjects Reporting at Least One Adverse Event	n (%)	n	n (%)	n	n (%)	n
System Organ Class 1	n (%)	n	n (%)	n	n (%)	n
Preferred Term 1	n (%)	n	n (%)	n	n (%)	n
Preferred Term 2	n (%)	n	n (%)	n	n (%)	n
.						
.						
System Organ Class 2	n (%)	n	n (%)	n	n (%)	n
Preferred Term 1	n (%)	n	n (%)	n	n (%)	n
Preferred Term 2	n (%)	n	n (%)	n	n (%)	n

Note: Post-treatment adverse events are defined as TEAEs that have an onset more than 14 days after the last dose of study drug.

 At each level of summation (overall, system organ class, preferred term), subjects reporting more than one adverse event are counted only once.

path\t\_program.sas date time

*Programming Note: Repeat table for Table 14.3.2.15.2 Post-Treatment Adverse Events by System Organ Class and Preferred Term – Non-AChEI/Memantine Users (Safety Population)*

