4.3 Duration

The study will continue until alternate options for access to treatment are available, *i.e.*, commercialization or, depending on country, on a Named Patient or compassionate basis, or availability *via* a Managed Access Program. (See Section 5.4 for a discussion of other reasons for study termination.)

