A follow-up visit will be performed approximately 28 (± 14) days after the last dose of study drug for those subjects who do not wish to continue with open-label treatment.

The following assessments will be performed:

- Blood pressure and pulse measured with subject in a seated position for at least 5 minutes
- Respiratory rate and preferably oral (sublingual) temperature; aural temperature is an acceptable, but less preferable, alternative
- Concomitant medication recording/review
- Adverse events review
- Blood samples for the following tests:
 - Chemistry panel
 - Hematology panel
 - Serum pregnancy test for women of childbearing potential only
- Body weight
- 12-lead ECG measurements performed in triplicate (three ECG tracings within an approximate 5-minute interval)
- Physical and neurological examination (includes an assessment for signs and symptoms of serotonin toxicity)
- MMSE

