#### 4.1 Conventions

The precision of original measurements will be maintained in summaries, when possible. Means, medians and standard deviations will be presented with an increased level of precision; means and medians will be presented to one more decimal place than the raw data, and the standard deviations will be presented to two more decimal places than the raw data.

---

 Mapped data consists of medical history, concomitant medication, and AE data obtained during the prior studies and imported into the 020 database (for handling of these data see Sections 5.5, 5.6, and 7.1, respectively).

Unless otherwise specified, summaries of continuous variables that have some values recorded using approximate values (e.g., < or >) will use imputed values. The approximate values will be imputed using the closest exact value for that measurement. For tables where rounding is required, rounding will be done to the nearest round-off unit. For example, if the round-off unit is the ones place (i.e., integers), values  $\geq XX.5$  will be rounded up to  $XX+1$  while values  $< XX.5$  will be rounded down to  $XX$ .

For percentages, unless they are calculated to be exactly 0% or 100%, values of very small or very large percentages will be reported as  $<0.1\%$  and  $>99.9\%$ .

For by-visit tables, percentages will be based on available data and denominators will generally exclude subjects with missing values. For frequency counts of categorical variables, categories whose counts are zero will be displayed for the sake of completeness. For example, if none of the subjects discontinue due to “lost to follow-up”, this reason will be included in the table with a count of 0.

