### **5. STUDY POPULATION**

#### **5.1 Analysis Population**

The safety population is defined as all subjects who received at least one dose of LMTM in 020. Subjects dispensed study medication who subsequently are lost to follow up without any contact are not included in the Safety Population but will be included in the study disposition tabulation and listings. With the exception of study disposition, all tables and listings will be generated on the basis of the Safety Population.

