## **7. SAFETY ANALYSES**

### **7.1 Adverse Events**

There are two CRFs contributing adverse event data.

- **Prior Study – Adverse Events CRF:** All adverse events as recorded during prior studies 005, 007 and 015 will be automatically uploaded to the Prior Study – Adverse Events CRF and adverse events recorded during the 008 study will be recopied from the 008 records by the site to the Prior Study – Adverse Events CRF. The only field that can be modified by the site is the OLEX end date as applicable. Additionally there is a comment field where text can be entered by site.
- **Adverse Event CRF:** New adverse events or changes to an existing adverse event will be recorded on the Adverse Event CRF.

Adverse events will be coded to SOC and PT using MedDRA (version 16.0). The coding process is described in the Data Management Plan.

AEs are grouped as follows and source(s) of data identified:

1. **Prior AEs:** AEs that were ongoing at the end of the prior study but that resolved before Day 1 of dosing in 020 or that started and resolved during the gap between studies. The source would be both the Prior Study – Adverse Events CRF and the (020) Adverse Event CRF.
2. **Pre-existing AEs:** AEs that were ongoing on Day 1 of dosing in 020 - source is the Prior Study – Adverse Events CRF. The source would be both the Prior Study – Adverse Events CRF and the (020) Adverse Event CRF.

3. Study-emergent AEs: AEs that started on or after Day 1 of dosing in 020, excluding post-treatment AEs (defined in #5 below). The source would be the (020) Adverse Event CRF.
4. All AEs: Whether pre-existing or study-emergent (merge of AEs that were ongoing on Day 1 of dosing) excluding post-treatment AEs. Sources are the Prior Study – Adverse Events CRF and the (020) Adverse Event CRF (note, this is a merge of #2 and 3 above *only*).
5. Post-treatment AEs: The study-emergent AEs (3# above) that have an onset more than 14 days after the last dose of study drug or that worsen in intensity or treatment attribution following discontinuation more than 14 days after the last dose of study drug.

The tabular summaries will be provided for AEs, with the number and percentage of subjects reporting each type of event. If a subject reports the same preferred term more than once, it is counted only once within that category. Further, for a given tabulation, the preferred term will only be counted once at its worst severity and strongest relationship to treatment.

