- Number of subjects who experienced unique protocol-specified AESIs and total number of unique protocol-specified AESIs by MedDRA SOC and PT.

The above summaries of AEs will also be presented for non-AChEI (acetylcholinesterase inhibitor)/Memantine users. Selected summaries of AEs will also be presented by diagnosis and prior study treatment. Depending on controlled study results, analyses of selected TauRx AE groupings may be undertaken.

A tabular summary of post-treatment adverse events (#5 above) by MedDRA SOC and PT will be provided.

The AE listing will include Prior AEs, All AEs, and Post-treatment AEs (#1, 4, and 5 above). Prior AEs, Pre-existing AEs and Post-treatment AEs will be flagged.

In addition, listings will also be provided for study-emergent or post-treatment SAEs (including subsets for fatal and non-fatal SAEs), study-emergent AEs leading to dose reduction, interruption or study drug withdrawal, and study-emergent or post-treatment AESIs. Post-treatment AEs will be flagged.

---

 Relationship is determined by the Investigator

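### The post-treatment AE tables divide by the whole Safety Population, although only subjects off LMTM and observed beyond the cut-off can contribute, so their percentages are biased low by an unstated and possibly small amount

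*SAP*

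**What the plan says.** SAP 7.1 sorts adverse events into groups. Group 5, post-treatment AEs, covers events that "have an onset more than 14 days after the last dose of study drug or that worsen in intensity or treatment attribution" more than 14 days after the last dose. Groups 3 (study-emergent) and 4 (all AEs) exclude group 5. For group 5 the SAP plans this output: "A tabular summary of post-treatment adverse events (#5 above) by MedDRA SOC and PT will be provided". The shell is Table 14.3.2.15.1, labelled Safety Population, with (N= ) column headers and n (%) cells. Table 14.3.2.15.2 repeats it for non-AChEI/memantine users. The shell's note gives only the onset part of the definition: "Post-treatment adverse events are defined as TEAEs that have an onset more than 14 days after the last dose of study drug".

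The denominator comes from three places:

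- SAP 5.1: "With the exception of study disposition, all tables and listings will be generated on the basis of the Safety Population".
- SAP 5.1 again: "The safety population is defined as all subjects who received at least one dose of LMTM in 020".
- SAP 4.1, the one general rule that takes unobserved subjects out of a denominator: "For by-visit tables, percentages will be based on available data and denominators will generally exclude subjects with missing values". The post-treatment AE tables are not by visit.

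The planned observation off drug is one visit. Protocol Appendix A says: "A follow-up visit will be performed approximately 28 (± 14) days after the last dose of study drug for those subjects" who do not continue. Protocol 4.1 and 4.4 and SAP 3 extend the visit to everyone who ceases LMTM, whatever the reason, and SAP 3.1 says it should be scheduled for all subjects. Protocol 9 allows interim reports before the study ends.

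**The concern.** The numerator and denominator describe different groups. To be counted, a subject must have a last dose and must still be under observation after the cut-off. The column total requires only a first dose. It therefore includes subjects who died on drug, subjects lost or withdrawn before the cut-off, and subjects whose follow-up visit fell on Day 14, which the window permits. In an interim report it also includes everyone still on treatment. These subjects cannot contribute an event, but they lower the percentage.

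Because groups 3 and 4 exclude these events, the two tables are the only AE tables in which events after the cut-off appear; elsewhere they are only listed. A reader who takes the printed percentage as the frequency of late off-drug events would read it too low, and nothing on the page gives the number observed.

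**Working it through.** The plan states no post-treatment AE rate and no number at risk, so there is no figure of its own to reproduce.

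**Inputs**

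- Cut-off: more than 14 days after last dose (SAP 7.1 and the table note); more than 7 days in protocol 9.6.1.
- Follow-up visit: 28 ± 14 days after last dose (protocol Appendix A), so Day 14 to Day 42.
- Anticipated N: 1050 to 1400 (protocol 4.2).
- f, the share of the column N that is off LMTM and observed beyond the cut-off: not given in the documents, so assumed over a range.

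**Step 1: observation time from the follow-up visit.** Days beyond the cut-off = visit day − cut-off.

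- SAP cut-off: 14 − 14 = 0; 28 − 14 = 14 (nominal); 42 − 14 = 28.
- Protocol cut-off: 14 − 7 = 7; 28 − 7 = 21 (nominal); 42 − 7 = 35.

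Under the SAP cut-off, a visit at the early edge of the window gives no post-treatment AE observation. The number at risk therefore depends on which cut-off applies.

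**Step 2: size of the shortfall.** With x subjects having an event, the printed percentage is x/N and the percentage among those observed is x/(f × N). Hence printed = f × observed. The relative shortfall is 1 − f and the correction factor is 1/f. N cancels.

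Example with N = 1400 and f = 0.90: 1260 subjects are observed. If 126 have an event, the percentage among those observed is 126/1260 = 10%, and the table prints 126/1400 = 9.0%.

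For an illustrative 10% among those observed:

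| Assumed f | Printed | Relative shortfall | Factor 1/f |
|---|---|---|---|
| 1.00 | 10% | 0% | 1.00 |
| 0.95 | 9.5% | 5% | 1.05 |
| 0.90 | 9.0% | 10% | 1.11 |
| 0.75 | 7.5% | 25% | 1.33 |
| 0.50 | 5.0% | 50% | 2.00 |
| 0.25 | 2.5% | 75% | 4.00 |

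The first three rows are plausible at final lock if attendance is good. The lower rows illustrate an interim cut with many subjects still on drug, or heavy loss of follow-up. No document supports any particular row.

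**Step 3: comparison within the SAP.** The shell for potentially clinically significant laboratory values (Table 14.3.3.3.1) defines its n as subjects with a result at that visit. The haematology shell (Table 14.3.3.1.1) restricts its by-visit baseline to subjects assessed at that visit. Laboratory summaries thus use observed denominators, while AEs from the same follow-up visit do not.

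**The case against.** The strongest reply is that the plan already asks for follow-up of everyone who stops, for any reason. At final lock all dosing in this study has ended, so f could be close to 1 and the shortfall trivial. Using the Safety Population for AE tables is also conventional and is prespecified in protocol 9.3.1. Counts are printed beside the percentages, and the disposition tables and visit-date listing let a careful reader approximate the number at risk. The shell has no percentage footnote, so the denominator is itself inferred from the title, headers and SAP 5.1.

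This limits the size of the problem but not its direction. No passage sets an at-risk denominator for these tables, and f can equal 1 only if every treated subject stopped and was seen past the cut-off.

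A reader might infer more than the documents support:

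- **That the percentages are 30% to 50% too low.** This needs f of 0.7 to 0.5, which nothing in the plan indicates.
- **That these are the only tabulations of any off-drug event.** AEs starting in the first 14 days off drug fall in the study-emergent group and appear in its tables. Later events are also flagged in the AE, SAE and AESI listings, and post-treatment laboratory results are summarised under SAP 7.2.
- **That AD and bvFTD columns, or AChEI/memantine subgroups, cannot be compared.** The same follow-up rule applies to all, no difference in attendance is shown, and protocol 9.3.2 plans no inferential statistics.
- **That subjects moving to commercial or managed access have no follow-up.** Protocol 4.3 says only when the study ends: "The study will continue until alternate options for access to treatment are available". Whether these subjects count as ceasing LMTM is left open, and SAP 3.1 points towards scheduling the visit for them too.

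**Conclusion.** The point holds as a denominator mismatch with a known direction and an unknown, possibly small, size. The percentages in Tables 14.3.2.15.1 and 14.3.2.15.2 equal f times the percentage among subjects observed beyond the cut-off. If f is 0.90 to 0.95 at final lock, an assumption, the shortfall is 10% to 5% in relative terms. It would be larger in any interim report that uses these shells, or if many subjects miss follow-up. Counts are unaffected.

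The conclusion assumes that the column N is the printed denominator, as the title, headers and SAP 5.1 indicate. The factor f describes the gap from the percentage among those observed; it says nothing about what would have been seen in the unobserved subjects. The case for changing the tables is that the change is cheap and matches the SAP's laboratory practice, not that a large distortion has been shown.

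**What to change.** 1. Reconcile the post-treatment cut-off. Protocol 9.6.1 uses more than 7 days and SAP 7.1 more than 14, and SAP Section 9 does not identify this as a change. Align the table note with SAP 7.1 group 5, which also counts worsening in intensity or attribution after the cut-off. The number at risk cannot be defined until this is settled.
2. In both tables, use as denominator the subjects with a documented visit or contact beyond the reconciled cut-off, and show that n in the column header.
3. Add total off-drug person-days beyond the cut-off, since observation per subject varies with the visit date.
4. If wanted, keep n/N(Safety) as a labelled secondary column.

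The cost is SAP and shell wording and a little programming. The last-dose date is on the Study Exit Status form (SAP 4.3 and 6), visit dates are already listed (Listing 16.2.1.3), and SAP 4.3 already uses the last day of study contact. The visible consequence is somewhat higher reported percentages.

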**Table 14.3.3.1.1.1**  
**Hematology Values and Changes from Baseline at All Visits – Conventional Units**  
**Safety Population**

Laboratory Parameter	Target Visit	AD (N= )	bvFTD (N= )	All Subjects (N= )
Hematocrit (%)	Baseline 			
	n	n	n	n
	Mean (SD)	xx.x (xx.xx)	xx.x (xx.xx)	xx.x (xx.xx)
	Median	xx.x	xx.x	xx.x
	Min, Max	xx, xx	xx, xx	xx, xx
	By-visit Baseline for Week 2 Visit 			
	N	n	n	n
	Mean (SD)	xx.x (xx.xx)	xx.x (xx.xx)	xx.x (xx.xx)
	Median	xx.x	xx.x	xx.x
	Min, Max	xx, xx	xx, xx	xx, xx
	Week 2			
	N	n	n	n
	Mean (SD)	xx.x (xx.xx)	xx.x (xx.xx)	xx.x (xx.xx)
	Median	xx.x	xx.x	xx.x
	Min, Max	xx, xx	xx, xx	xx, xx
	Change from Baseline to Week 2			
n	n	n	n	
Mean (SD)	xx.x (xx.xx)	xx.x (xx.xx)	xx.x (xx.xx)	
Median	xx.x	xx.x	xx.x	
Min, Max	xx, xx	xx, xx	xx, xx	
...				
Hemoglobin (g/dL)				
.				
.				

 Baseline is defined as the last non-missing value prior to first dose of study drug.

 By-visit Baseline is defined as the baseline assessments from subjects with a non-missing assessment at that visit.

path\t\_program.sas date time

*Programming note: Table will include all hematology parameters collected from Central Laboratory, and all target visits and for Last Available On-Treatment Value. Please see Appendix A for visit windows.*

*Programming Note: Repeat table for the tables listed below*

*Table 14.3.3.1.1.2 Hematology Values and Changes from Baseline at All Visits – Conventional Units – Non-AChEI/Memantine Users (Safety Population)*

- Table 14.3.3.1.2.1 Hematology Values and Changes from Baseline at All Visits – SI Units (Safety Population)*
- Table 14.3.3.1.2.2 Hematology Values and Changes from Baseline at All Visits – SI Units – Non-AChEI/Memantine Users (Safety Population)*

**Table 14.3.3.2.1.1**  
**Serum Chemistry Values and Changes from Baseline at All Visits – Conventional Units**  
**Safety Population**

Laboratory Parameter	Target Visit	AD (N= )	bvFTD (N= )	All Subjects (N= )
Sodium (mEq/L)	Baseline 			
	n	n	n	n
	Mean (SD)	xx.x (xx.xx)	xx.x (xx.xx)	xx.x (xx.xx)
	Median	xx.x	xx.x	xx.x
	Min, Max	xx, xx	xx, xx	xx, xx
	By-visit Baseline for Week 2 Visit 			
	N	n	n	n
	Mean (SD)	xx.x (xx.xx)	xx.x (xx.xx)	xx.x (xx.xx)
	Median	xx.x	xx.x	xx.x
	Min, Max	xx, xx	xx, xx	xx, xx
	Week 2			
	N	n	n	n
	Mean (SD)	xx.x (xx.xx)	xx.x (xx.xx)	xx.x (xx.xx)
	Median	xx.x	xx.x	xx.x
	Min, Max	xx, xx	xx, xx	xx, xx
	Change from Baseline to Week 2			
	n	n	n	n
	Mean (SD)	xx.x (xx.xx)	xx.x (xx.xx)	xx.x (xx.xx)
	Median	xx.x	xx.x	xx.x
	Min, Max	xx, xx	xx, xx	xx, xx
Potassium (mEq/L)	...			

 Baseline is defined as the last non-missing value prior to first dose of study drug.

 By-visit Baseline is defined as the baseline assessments from subjects with a non-missing assessment at that visit.

path\t\_program.sas date time

*Programming note: Table will include all serum chemistry parameters collected from Central Laboratory, and all target visits and for Last Available On-Treatment Value. Please see Appendix A for visit windows.*

*Programming Note: Repeat table for the tables listed below*

*Table 14.3.3.2.1.2 Serum Chemistry Values and Changes from Baseline at All Visits – Conventional Units – Non-AChEI/Memantine Users (Safety Population)*

*Table 14.3.3.2.2.1*  
*Table 14.3.3.2.2.2*

*Serum Chemistry Values and Changes from Baseline at All Visits – SI Units (Safety Population)*  
*Serum Chemistry Values and Changes from Baseline at All Visits – SI Units –*  
*Non-AChEI/Memantine Users (Safety Population)*

**Table 14.3.3.3.1**  
**Incidence of Potentially Clinically Significant Hematology and Serum Biochemistry Results**  
**Safety Population**

Laboratory Parameter	Potentially Clinically Significant Criteria	Target Visit	AD m/n (%)  (N= )	bvFTD m/n (%)  (N= )	All Subjects m/n (%)  (N= )
Hematology					
Hemoglobin	Criteria	Baseline	m/n (%)	m/n (%)	m/n (%)
		Any Post-Baseline PCS	m/n (%)	m/n (%)	m/n (%)
		Any Post-Baseline Worsening	m/n (%)	m/n (%)	m/n (%)
		Week 2	m/n (%)	m/n (%)	m/n (%)
		Week 13	m/n (%)	m/n (%)	m/n (%)
Serum Chemistry					
Sodium	Criteria	Baseline	m/n (%)	m/n (%)	m/n (%)
		Any Post-Baseline PCS	m/n (%)	m/n (%)	m/n (%)
		Any Post-Baseline Worsening	m/n (%)	m/n (%)	m/n (%)
		Week 2	m/n (%)	m/n (%)	m/n (%)
		Week 13	m/n (%)	m/n (%)	m/n (%)

Note: ULN = Upper Limit of Normal.

 m: number of subjects with at least one potentially clinically significant result at corresponding visit; n: number of subjects with at least one non-missing result at corresponding visit.

Note: For the post-Baseline visits, only subjects in whom the values represent a treatment-emergent worsening from Baseline (i.e. more out of range) are summarized.

path\t\_program.sas date time

*Programming note: Table will include all parameters with defined potentially clinically significant ranges at each post-Baseline visit and for Last Available On-Treatment Value. Please see Appendix A for target visits and visit windows. Ensure that criteria indicating an increase or a decrease are presented separately.*

*Programming Note: Repeat table for Table 14.3.3.3.2 Incidence of Potentially Clinically Significant Hematology and Serum Biochemistry Results – Non-AChEI/Memantine Users (Safety Population)*

